6.1 Sample Size

To achieve 95% power at the 5% level for the primary objective (assuming a change of 0.72 hour in the Circadin® arm and 0.27 hour in the placebo arm and a standard deviation (SD) of 0.69 in the Circadin® arm and 0.45 in the placebo arm), 45 subjects are required per combined group. Therefore, 90 subjects in total are required to complete Visit 5. These estimations are based on previous studies conducted with Circadin®.

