6.2 Randomization

At Visit 1, enough eligible male and female children, of ages 2 to 17.5 years, will be screened for the study to allow for 120 subjects to then be randomized in a 1:1 ratio to receive Circadin® or placebo at Visit 2. A minimum of 90 children are expected to complete the double-blind and first open-label period (up to Week 28). A minimum of 50 children are expected to complete the second open-label safety follow-up period.

7 Protocol Deviations

Major protocol deviations are defined as those deviations from the study protocol that may have the ability to impact the efficacy results. As such, subjects with major deviations occurring up to the end of the double-blind phase will be excluded from the per-protocol (PP) population (as defined in Section 8.5).

Major protocol deviations include (but are not limited to):

- Deviation from inclusion/exclusion criteria
- Withdrawal criteria met during the study but subject was not withdrawn
- Prohibited concomitant medications
- Substantial deviations from the dosing schedule (Subjects received at least 5 of 7 doses in the week prior to the scheduled visit and treatment compliance is within the range >60%)
- Substantial deviations in the completion of the sleep and nap diary (Subjects must have completed the diary at least 3 out of 7 nights per week over the two weeks prior to the scheduled visit and have a valid mean TST value at Visit 4)

Where possible, major deviations will be programmatically verified by Datatrial. Listings of concomitant medications in Excel format will be provided to the sponsor by Datatrial for review to identify prohibited medications prior to unblinding.

Major protocol deviations occurring up to the end of the first open-label phase will be identified during a Blinded Data Review Meeting (BDRM) prior to database lock and unblinding.

The purpose of the BDRM will be two-fold; It will be used to review and confirm the data identified as protocol deviations as detailed above. It will also be used to review the Sleep and Nap diary and confirm that the data is correct and/or identify implausible values and document any changes that are made to the source data. Blinded SAS listings of the Sleep and Nap diary data including derivation of mean TST will be provided by

Datatrial in advance of the BDRM to aid this review. Any changes to the source data may require a further review of the protocol deviations.

8 Analysis Populations

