11.3 Exploratory Efficacy Variables

11.3.1 Sleep and Nap Diary by Visit

The change from baseline at 3 weeks of double-blind treatment is analysed in the same model as the change from baseline at 13 weeks. From that model, the adjusted mean change from baseline (and standard error) in TST after 3 weeks of treatment for each treatment group will be calculated and the associated 95% CI for the change presented. Furthermore, the estimated difference (and standard error) between treatments will be estimated, the associated 95% confidence interval presented and the null hypothesis that these means are equal will be tested.

For the TST during open-label treatment the estimated change from baseline (and standard error) will be calculated and associated 95% CI for the change will be presented for each visit. A paired t-test will be performed comparing the mean TST at visit to the baseline mean.

Example SAS code for this analysis is given below:

```
proc means data=tst mean stderr lclm uclm probt;  
  var chg;  
run;
```

These analyses will be repeated for the other sleep variables derived from the Sleep and Nap diary.

A subject is defined as a TST responder if the mean change from baseline in TST is 45 minutes or greater (increase in TST) over the 14 days prior to each scheduled visit. A subject is defined as a sleep latency responder if the mean change from baseline in sleep latency is 15 minutes or greater (reduction in SL) over the 14 days prior to each scheduled visit. Frequency tables of TST response and sleep latency response will be presented by scheduled visit.

For Visits 3 and 4, the TST response rate and sleep latency response rate will be analysed using logistic regression. Subjects without a mean TST (or mean sleep latency) at a visit will be taken to be non-responders in this analysis. The model will include terms for treatment and mean baseline value of TST and sleep latency respectively. From the model the estimated odds of responding will be calculated, as will estimated odds ratios, associated 95% CI and p-values for testing the null hypothesis of the odds ratio being 1.

Example SAS code for this analysis is given below:

```
proc genmod data=resp;  
  class trtp;  
  model resp=trtp base/link=logit dist=bin;  
  lsmeans trtp/diff cl om exp;  
run;
```

The responder analysis will be repeated on all non-missing data. That is, subjects without a mean TST (or mean sleep latency) at a visit will not be included in the analysis.

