11.3.2 Sleep Disturbance by Visit

For the sleep disturbance as assessed by the CSDI, the total CSDI score after 3 weeks of double blind treatment and during open-label treatment will be analysed as for TST.

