11.5 Missing Efficacy Data

11.5.1 Multiple Imputation

For the primary efficacy variable and the secondary efficacy variables collected using the Sleep and Nap Diary, an analysis will be undertaken to assess the effect of missing data arising on the estimated treatment effects. This will be done using a pattern mixture model where missing data from subjects who are withdrawn is imputed with observations imitating the placebo response [2].

Specifically, using the absolute values for baseline, Week 5 and Week 15, a monotone multiply imputed (1000 imputations) dataset will be initially created. Using this dataset the remaining missing data will then be imputed (1 imputation) using an imputation model based on sequential regression methodology. Starting at Week 5, values for subjects that have missing data will be imputed based on all placebo-treated subjects having a value at that visit. The effect of this is to mimic the expected response as if the withdrawn subjects had been treated with placebo from the point of withdrawal. Next, at Week 15, values for subjects that have missing data will be imputed based on all placebo-treated subjects having a value at that visit. The change from baseline to Week 15 will then be calculated.

These imputed datasets will be analysed separately using ANCOVA with randomised treatment as a factor and baseline as a covariate. The individual results will then be combined using the method of Rubin [3]. The adjusted mean change from baseline (and standard error) in TST after 13 weeks of treatment for each treatment group, the estimated difference (and standard error) between treatments, the associated 95% CI presented and the p-value for the test of null hypothesis that these means are equal will be presented.

Example SAS code for this analysis is given below:

```
* Create monotone dataset;
proc mi data=tst out=mi_mono nimpute=1000 seed=5635245;
  by trtp;
  var week_0 week_3 week_13;
  mcmc impute=monotone;
run;

* Pattern mixture model with placebo-based imputation;
* Impute week 3;
data mi_impl mi_rest1;
  set mi_mono;
```

```
if trtp='Circadin' and lastwk>=3 then output mi_rest1;
else output mi_imp1;
run;

proc mi data=mi_imp1 out=mi_reg_imp1 nimpute=1 seed=8254340;
  class gender disease;
  var week_0 week_3;
  monotone regression;
  by _imputation_;
run;

data midata_2;
  set mi_rest1 mi_reg_imp1;
  by _imputation_;
run;

* Impute week 13;
data mi_imp2 mi_rest2;
  set midata_2;

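### Exploratory open-label change is tested on observed cases, visit by visit, with no missing-data handling after Week 15, so the maintenance estimates may describe a selected group

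*SAP*

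**What the plan says.** For open-label TST, SAP 11.3.1 estimates the change from baseline, with the "associated 95% CI for the change will be presented for each visit", and then tests it: "A paired t-test will be performed comparing the mean TST at visit to the baseline mean". The example code is a PROC MEANS step on the change variable, so only non-missing values count. The section repeats this for the other diary variables. SAP 11.3.2 adds that "the total CSDI score after 3 weeks of double blind treatment and during open-label treatment will be analysed as for TST", and 11.3.3 to 11.3.7 do likewise for CGAS and SDQ (Week 28) and for ESS, PSQI and WHO-5. By Protocol Table 5-2 the diary stops at Visit 7 (Week 54), while CSDI, ESS, PSQI and WHO-5 continue to Weeks 106 and 108.

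The missing-data provisions are these:

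- SAP 11.5.1 imputes "using the absolute values for baseline, Week 5 and Week 15".
- SAP 11.5.2 applies BOCF in the same ANCOVA, and the BOCF tables listed in 16.1 are all for 13 weeks double blind.
- SAP 11.3.1 counts a missing child as a non-responder only in the logistic regression for Visits 3 and 4. The open-label responder frequencies have no rule.
- Protocol 12.11 does not replace missing primary or secondary data.

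On retention, SAP 6.2 screens enough children "to allow for 120 subjects to then be randomized in a 1:1 ratio", expects at least 90 to reach Week 28, and adds: "A minimum of 50 children are expected to complete the second open-label safety follow-up period". Protocol Section 7 names maintenance of efficacy, together with safety, as a purpose of both open-label periods.

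**The concern.** A child who leaves during open-label treatment drops out of the diary estimate at every later visit, so the set of children tested can change from one visit to the next. If children who respond poorly are more likely to leave, the mean change can hold steady or rise because the denominator shrinks. A reader would take that as maintained benefit.

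The SAP protects the double-blind phase against this, but the floors allow further loss afterwards, where there is no protection. Protocol 12.8.1 planned only descriptive open-label summaries. The SAP adds confidence intervals and tests without extending the missing-data provisions, and its Section 14 on changes mentions only the move of CSDI.

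**Working it through.** **The plan's own figure.** Inputs from SAP 6.1 ("To achieve 95% power at the 5% level for the primary objective"): changes 0.72 and 0.27 h, SDs 0.69 and 0.45 h. Sidedness is not stated; two-sided is assumed.

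n per group = (1.960 + 1.645)² × (0.69² + 0.45²) / (0.72 − 0.27)² = 12.996 × 0.6786 / 0.2025 = 43.55, so 44 by the normal approximation. With the t distribution, 44 per group gives 94.8% power and 45 gives 95.2%. The stated 45 per group, 90 in total, is reproduced, and 90 / 0.75 = 120.

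**Floors.** 90/120 = 75% to Week 28 and 50/120 = 42% to Week 106. With 90 at Week 28, up to 90 − 50 = 40 children could leave before Week 106 without breaching the floor.

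**Illustration for TST at Week 54.** The documents give no number for Week 54, so three assumptions are needed:

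- Loss from 90 to 50 is linear between Weeks 28 and 106: 90 − 40 × (54 − 28)/(106 − 28) = 90 − 40 × 26/78 = 76.7, about 77 stayers and 13.3 leavers.
- Stayers gain the planned 0.72 h.
- Leavers have change x: equal to stayers (0.72), the planned placebo change (0.27), or none (0).

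Mean over the 90 = (76.7 × 0.72 + 13.3 × x) / 90.

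| x (h) | Mean over 90 (h) | Observed-case estimate (h) | Gap |
|---|---|---|---|
| 0.72 | 0.72 | 0.72 | 0 |
| 0.27 | (55.2 + 3.6)/90 = 0.65 | 0.72 | 0.07 h (4 min) |
| 0 | 55.2/90 = 0.61 | 0.72 | 0.11 h (6 min) |

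With L leavers the gap is (L/90) × (0.72 − x). It is zero if nobody leaves and changes sign if leavers do better than stayers. If all 40 had already gone by Week 54, it would be 40/90 × 0.45 = 0.20 h or 40/90 × 0.72 = 0.32 h. That is an outer limit of this illustration, not an expectation.

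**What the test would show.** With SD 0.69 h, the observed-case t is 0.72 / (0.69/√76.7) = 9.1. With leavers at zero, the SD over the 90 is √[0.852 × (0.69² + 0.72²) − 0.613²] = 0.686 and t = 0.613 / (0.686/√90) = 8.5. Both reject. In this illustration selection alters the estimated gain and leaves the significance result unchanged.

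Rejection is also weak evidence of a drug effect: the planned placebo change alone gives 0.27 / (0.45/√45) = 4.0, p = 0.0002.

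**The case against.** The case for leaving the plan alone has real content.

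- **Status.** These analyses are exploratory. The primary Week 15 comparison is untouched and already has MI and BOCF. SAP 9.2 limits open-label tables in the main report to Visit 5, and later data go into an appendix to the CSR.
- **Visibility.** The number of children is part of every summary (SAP 9.1), and starters, completers and reasons for leaving are tabulated for each open-label phase (SAP 10.1).
- **Limits of any remedy.** The tests compare with pre-treatment baseline and have no control. A repeated-measures model assumes data are missing at random, and a zero change for leavers is itself an assumption.

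All of this stands. It limits the weight of the point, but the efficacy estimates still have no rule for leavers.

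A reader might also infer more than the documents support:

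- *That the plan forecasts a fall from 120 to 90 to 50.* Both lower figures are stated minimums, and the 50 belongs to Week 106, after the last TST diary.
- *That the gain should be averaged over all 120 randomised.* That would count children who left in the double-blind phase, including placebo children who never took open-label drug.
- *That a percentage overstatement at Week 106 can be calculated.* TST is not collected then, and the scales that are have other units and no planned effect sizes.
- *That leavers have no score on any outcome.* Protocol 6.3 and 11.3 call for a withdrawal visit with the Section 8.19 procedures, which include CSDI, ESS, PSQI and WHO-5. For these the gap is that the SAP does not say how the withdrawal-visit value is used. The diary, CGAS and SDQ are not in 8.19.
- *That the bias must be upward.* The documents do not say why children would leave.

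**Conclusion.** The concern holds for the exploratory open-label analyses. They are separate observed-case tests, no missing-data handling applies after Week 15, and maintenance is a stated aim under floors that allow substantial loss. If leaving depends on response, the estimates describe a selected group.

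Neither direction nor size is known. The only illustration offered is 0.65 or 0.61 h against 0.72 h for TST at Week 54. It rests on the floors being met exactly, linear loss, stayers at the planned gain and assumed leaver scores. No size can be given for Visit 5, the one open-label visit in the main report, because the documents do not say how many children will be supplied with drug at Visit 4. This is a modest, inexpensive improvement and does not threaten the primary result.

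**What to change.** In SAP 11.3.1, and by reference in 11.3.2 to 11.3.7:

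1. Estimate open-label change at each visit from one MMRM over all post-baseline visits with data, with unstructured covariance and visit by randomised arm. Keep the paired t-test only as a result labelled observed-case, shown with n/N, where N is the children supplied with open-label drug at Visit 4 (SAP 10.1 already defines starters this way).
2. Because the MMRM assumes missing at random, add one sensitivity row for all children supplied with open-label drug. Use the withdrawal-visit score where it was collected (CSDI, ESS, PSQI, WHO-5) and BOCF otherwise.
3. In the open-label responder tables, use the same children as denominator and count missing as non-response, as already done for Visits 3 and 4.

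The cost is a little more output, built largely from code already in the SAP, and open-label figures that are likely to look somewhat less favourable. None of this supplies a control group, so the results remain within-group changes.

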8.4 Full Analysis Set

Efficacy analyses will be performed on the Full Analysis Subset (FAS), and will include all subjects in the Safety Analysis Set who satisfy all major entry criteria (Inclusion Criteria 1-5) and who have a valid mean TST result recorded for baseline and at least one post-baseline period assessment during the double blind phase. Subjects will be classified according to randomized treatment. This analysis set will be used for all efficacy analyses.

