10.6 Prior and Concomitant Medications

Concomitant medications recorded during the study will be coded using World Health Organization (WHO)-Drug. Details of concomitant medication will be listed.

Concomitant medications will be summarized according to whether they were being taken pre-study (prior medications) and/or during the study (concomitant medication). Prior medications are any that were being taken prior to the first dose of study medication (medication stop date prior to the first dose of study medication). Concomitant medications are any that were being taken on or after the first dose of study medication. If the start and stop dates of the concomitant medications do not clearly define the period during which a medication was taken, it will be assumed to be a concomitant medication.

Concomitant medications will be assigned to the phase they were taken: Double-Blind, first Open-Label, second Open-Label. If a concomitant medication starts or is ongoing between Visit 2 and Visit 4, it will be assigned to the Double-Blind phase. If a concomitant medication starts or is ongoing between Visit 4 + 1 day and Visit 5, it will be assigned to the first Open-Label phase. If a concomitant medication starts or is ongoing between Visit 5 + 1 day and Visit 8, it will be assigned to the second Open-Label phase. If the start and stop dates of the concomitant medications do not clearly define the phase during which a medication was taken, it will be assumed to be taken across all phases.

Prior and concomitant medications will be summarized by Anatomical Therapeutic Chemical (ATC) level 2 term and preferred term.

Details of non-pharmacological concomitant measures will be listed.

11 Efficacy

Subjects will be classified and summarized by randomized treatment. For all efficacy assessments, the baseline values will be calculated as the last recorded value prior to the start of randomized treatment. Change from baseline values will be calculated as the assessment score minus the baseline value. For questionnaires the change from baseline values will be calculated for each item and total/subscale score as applicable.

All summaries and analyses will be performed on the FAS set. The primary efficacy endpoint and select secondary efficacy endpoints will also be analyzed on the PP set. Analyses looking at the impact missing data on the primary efficacy endpoint will also be performed on the All Randomized set.

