11.1 Primary Efficacy Variable

11.1.1 Total Sleep Time (TST)

TST will be assessed by a Sleep and Nap Diary.

Daily TST will be calculated programmatically as follows:

the time the child woke up in the morning *minus*

the time the child went to bed *minus*

the time taken to fall asleep *minus*

the total duration of any night awakenings

If the time the child went to bed and the time they woke up in the morning are the same, the TST will be set to 0.

The number of daily diaries with data recorded and the number of daily diaries with a valid mean TST will be tabulated by scheduled visit.

For each subject the mean TST will then be calculated as the mean of the last 14 days prior to each scheduled visit. A subject will be required to have a minimum of 3 nightly TST values per week (6 nights in total) in order to have a valid mean TST after baseline. A subject will be required to have a minimum of 6

nightly TST values across the 2 weeks in order to have a valid mean TST at baseline. The mean TST and change from baseline in mean TST will be summarized by scheduled visit using descriptive statistics. The change from baseline in mean TST will be plotted over time. Empirical cumulative distribution functions by treatment group will be plotted for change from baseline in mean TST at Visit 4 (Week 15).

The change from baseline in mean TST will be analyzed using a mixed-effects model for repeated-measures (MMRM). The model will contain the TST at Visit 3 (Week 5) and Visit 4 (Week 15) as the dependent variable, with fixed effects for visit, the mean baseline TST, randomized treatment and the mean baseline TST and randomised treatment both nested within visit. Visit-to-visit repeated measures will assume a general (unstructured) covariance structure. Standard errors and degrees of freedom for significance tests will be derived using the Kenward-Roger method [1].

From this model, the adjusted mean change from baseline (and standard error) in TST after 13 weeks of treatment for each treatment group will be calculated and the associated 95% confidence intervals (CI) for the change presented. Furthermore, the estimated difference (and standard error) between treatments will be estimated, the associated 95% CI presented and the null hypothesis that these means are equal will be tested.

Example SAS code for this analysis is given below:

```
proc mixed data=tst method=reml;
  class subjid trtp avisitn;

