Table 14.2.5.12	Actigraphy Sleep Efficiency Change from Baseline at 13 Weeks Double Blind – MMRM Analysis	FAS Set
Table 14.2.6.1	SND Total Sleep Time Change from Baseline at 3 Weeks Double Blind – MMRM Analysis	FAS Set
Table 14.2.6.2	SND Total Sleep Time and Change from Baseline – Open Label - Descriptive Statistics	FAS Set
Table 14.2.6.3	SND Total Sleep Time Change from Baseline Analysis During the Open Label Phase	FAS Set
Table 14.2.6.4	SND Sleep Latency Change from Baseline at 3 Weeks Double Blind – MMRM Analysis	FAS Set
Table 14.2.6.5	SND Sleep Latency and Change from Baseline – Open Label - Descriptive Statistics	FAS Set
Table 14.2.6.6	SND Sleep Latency Change from Baseline Analysis During the Open Label Phase	FAS Set
Table 14.2.6.7	SND Duration of Wake Change from Baseline at 3 Weeks Double Blind – MMRM Analysis	FAS Set

Table Number	Table Title	Population
Table 14.2.6.8	SND Duration of Wake and Change from Baseline – Open Label - Descriptive Statistics	FAS Set
Table 14.2.6.9	SND Duration of Wake Change from Baseline Analysis During the Open Label Phase	FAS Set
Table 14.2.6.10	SND Number of Awakenings Change from Baseline at 3 Weeks Double Blind – MMRM Analysis	FAS Set
Table 14.2.6.11	SND Number of Awakenings and Change from Baseline – Open Label - Descriptive Statistics	FAS Set
Table 14.2.6.12	SND Number of Awakenings Change from Baseline Analysis During the Open Label Phase	FAS Set
Table 14.2.6.13	SND Longest Sleep Period Change from Baseline at 3 Weeks Double Blind – MMRM Analysis	FAS Set
Table 14.2.6.14	SND Longest Sleep Period and Change from Baseline – Open Label - Descriptive Statistics	FAS Set
Table 14.2.6.15	SND Longest Sleep Period Change from Baseline Analysis During the Open Label Phase	FAS Set
Table 14.2.6.16	SND Total Time in Bed Change from Baseline at 3 Weeks Double Blind – MMRM Analysis	FAS Set
Table 14.2.6.17	SND Total Time in Bed and Change from Baseline – Open Label - Descriptive Statistics	FAS Set
Table 14.2.6.18	SND Total Time in Bed Change from Baseline Analysis During the Open Label Phase	FAS Set
Table 14.2.6.19	SND TST Response – Logistic Regression	FAS Set
Table 14.2.6.20	SND Sleep Latency Response – Logistic Regression	FAS Set
Table 14.2.6.21	SND TST Response – Logistic Regression (Non-Missing Data)	FAS Set
Table 14.2.6.22	SND Sleep Latency Response – Logistic Regression (Non-Missing Data)	FAS Set
Table 14.2.6.23	SND Shift in Time to Bed by Scheduled Visit	FAS Set

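### The TST and sleep latency responder analyses that count missing data as non-response run on the FAS, which removes children with no valid mean TST at both Visit 3 and Visit 4

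*SAP*

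**What the plan says.** SAP 11.3.1 defines a TST responder by a mean increase of at least 45 minutes from baseline and a sleep latency responder by a mean reduction of at least 15 minutes. Response at Visits 3 and 4 is modelled by logistic regression on treatment and the baseline value. The missing-data rule is: "Subjects without a mean TST (or mean sleep latency) at a visit will be taken to be non-responders in this analysis". A second version follows: "The responder analysis will be repeated on all non-missing data".

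The population is set elsewhere. The introduction to SAP Section 11 states: "All summaries and analyses will be performed on the FAS set". The list of tables in SAP 16.1 agrees: the table titled "SND TST Response – Logistic Regression" (14.2.6.19), its sleep latency counterpart (14.2.6.20) and the two observed-data versions (14.2.6.21 and 14.2.6.22) all name the FAS.

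SAP 8.4 limits the FAS to dosed children who meet the first five inclusion criteria, and of these it takes only those "who have a valid mean TST result recorded for baseline and at least one post-baseline period assessment during the double blind phase". Under SAP 11.1.1 a post-baseline mean TST is valid only with at least 3 nightly values in each of the two diary weeks.

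For missing data the SAP also uses a wider set: "Analyses looking at the impact missing data on the primary efficacy endpoint will also be performed on the All Randomized set". SAP 8.2 and 11.5 and Tables 14.2.14.1 to 14.2.14.10 apply it to the multiple-imputation (MI) and baseline-carried-forward (BOCF) analyses of the continuous diary variables. No responder table uses it.

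**The concern.** Because a separate observed-data version exists, the role of the first version is to let missing data count against response. The FAS gate acts before that rule. The only double-blind post-baseline assessments are Visits 3 and 4, so on the FAS the TST rule can reach only a child who is missing exactly one of them. A child missing both would be a non-responder twice under the rule, but leaves the denominator.

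Visit 3 shows this most clearly. An FAS child without a valid Visit 3 TST must have a valid Visit 4 TST. At Visit 3 the TST rule therefore applies only to children who later supplied valid data, and never to one who left before Visit 3.

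Sleep latency has the same gate, because FAS membership depends on TST. SAP 11.2.1.1 states no minimum number of nights for latency, so on the text a child could have a mean latency and still be left out of Table 14.2.6.20.

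At stake are the reported response rates and odds ratios, which a reader would take to be conservative about dropout.

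**Working it through.** **The plan's own figure.** The SAP gives no figure for the responder analysis. Its sample size (SAP 6.1) is the source of the means and SDs used here, so I checked it first. The difference is 0.72 − 0.27 = 0.45 h and the average SD is √((0.69² + 0.45²)/2) = 0.5825 h. For two-sided 5% and 95% power, n = 2(1.960 + 1.645)² × 0.5825²/0.45² ≈ 43.6, so 44 per arm. With the t distribution it is 45 per arm, with power of 95.1% to 95.2%. The stated 45 reproduces. The point does not depend on it.

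**Who is counted at Visit 4 for TST**

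| Valid mean TST | In FAS? | Treated as |
|---|---|---|
| Visits 3 and 4 | Yes | Observed response |
| Visit 3 only | Yes | Non-responder |
| Visit 4 only | Yes | Observed response (non-responder at Visit 3) |
| Neither | No | Not in the analysis |

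**Inputs for the size**

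- Randomised: 120 in a 1:1 ratio, so 60 per arm (SAP 6.2).
- Mean changes 0.72 h and 0.27 h, SDs 0.69 h and 0.45 h (SAP 6.1).
- TST response threshold 45 min = 0.75 h (SAP 11.3.1).
- Assumption: changes are normally distributed.
- Assumption: k children per arm have no valid post-baseline TST. The documents do not give k. I use 0 to 15. At least 90 of 120 are expected to reach Week 28, so 30 may be lost, or 15 per arm if evenly split. That covers 13 weeks beyond the double-blind period, so I take it as an upper bound for dropout.
- Simplification: nobody is missing only one visit, and no one is excluded from the FAS for another reason.

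**Response probability among children with data**

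- Circadin: 1 − Φ((0.75 − 0.72)/0.69) = 0.483
- Placebo: 1 − Φ((0.75 − 0.27)/0.45) = 0.143

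On the FAS these rates hold for every k: 48.3% v 14.3%, difference 34.0 points, odds ratio 5.59. With all randomised children counted, each rate becomes p × (60 − k)/60. For example, at k = 3, 0.483 × 57/60 = 45.9%.

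| Lost, Circadin / placebo | Circadin | Placebo | Difference (points) | Odds ratio |
|---|---|---|---|---|
| FAS, any k | 48.3% | 14.3% | 34.0 | 5.59 |
| 3 / 3 | 45.9% | 13.6% | 32.3 | 5.38 |
| 6 / 6 | 43.4% | 12.9% | 30.6 | 5.20 |
| 15 / 15 | 36.2% | 10.7% | 25.5 | 4.72 |
| 9 / 3 | 41.0% | 13.6% | 27.4 | 4.42 |
| 3 / 9 | 45.9% | 12.2% | 33.7 | 6.12 |
| 15 / 0 | 36.2% | 14.3% | 21.9 | 3.40 |
| 0 / 15 | 48.3% | 10.7% | 37.5 | 7.76 |

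The contrast shifts even when loss is equal. With unequal loss it can go either way, and at 3 / 9 the difference falls while the odds ratio rises. The unadjusted z for the log odds ratio is 2.68 at 15 / 0 and 4.18 at 0 / 15, so under these assumptions nominal significance does not change.

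**The case against.** A reader might infer that the FAS discards the clearest treatment failures and so flatters the drug. The documents do not support that. A child with no valid post-baseline TST has an unknown outcome. Protocol 6.3 lists exits unrelated to efficacy, including consent withdrawal, a broken randomisation code and loss to follow-up. A child who takes the drug and sleeps well is also missing if the diary falls below 3 nights in either week. Such children are non-responders only by the SAP's convention, and if more of them are on placebo the FAS understates the contrast.

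A reader might also infer that the rule is empty, or that any family that stops the diary is lost. Neither is right. A child with a valid Visit 3 and no Visit 4 stays in the FAS and counts as a Visit 4 non-responder. That covers losses in the last 10 of the 13 double-blind weeks, provided the Visit 3 mean was valid.

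The strongest defence is that the SAP never promises to count every randomised child. The rule is written per visit, inside a section already assigned to the FAS. Early loss is also handled elsewhere: TST and sleep latency each have placebo-based MI and BOCF on the All Randomized Set, and double-blind dropout is compared between arms (SAP 11.2.5; Table 14.3.1.5, Safety Set). All of this stands, and it limits the consequence. It does not repair the responder tables, where a missing-data convention runs on a set already selected for having data.

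**Conclusion.** The point holds as a minor inconsistency in an exploratory analysis. In Tables 14.2.6.19 and 14.2.6.20, randomised children with no valid mean TST at both Visits 3 and 4 are removed and not counted as non-responders. For TST, that removal can only raise each arm's response rate relative to applying the SAP's rule to all randomised children. This cannot be said for latency, where a removed child might have an observed response.

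Under the assumptions above, equal loss of 3 to 15 per arm means the FAS overstates the Circadin rate by about 2 to 12 points and the difference by about 2 to 8 points. Unequal loss moves the odds ratio between 3.40 and 7.76, against 5.59 on the FAS. The ends of that range (15 v 0 and 0 v 15) are limits, not expectations. If few children are lost before Visit 3, the effect is small. The primary TST analysis is not affected.

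**What to change.** - Run Tables 14.2.6.19 and 14.2.6.20 on the All Randomized Set, restricted to children with a valid baseline value, because baseline is a covariate and a child without one would drop out of the model anyway.
- Amend the sentence in the introduction to SAP Section 11 that places all analyses on the FAS, so that it allows for these two tables.
- Keep the observed-data Tables 14.2.6.21 and 14.2.6.22 on the FAS.
- Report by arm how many randomised children the FAS excludes, and why.

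The cost is two population labels, one amended sentence, a stated baseline condition and one small table. Response rates will be slightly lower. The All Randomized Set also brings in any undosed child and any who failed Inclusion Criteria 1-5, so it changes slightly more than the missing-data handling; the exclusion table will show how many such children there are.
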